3.3.2 Exclusion Criteria

The following criteria will exclude a subject from participating in the study:

1. [REDACTED]
2. [REDACTED]
3. Presence of erythrodermic psoriasis, pustular psoriasis, guttate psoriasis, medication-induced psoriasis or other skin conditions (e.g., clinically-significant eczema or severe acne) that could interfere with study evaluations at Visit 1;
[REDACTED]
4. History or presence of any itch due to underlying conditions other than plaque psoriasis which cause or influence pruritus of the skin (e.g., drug-induced pruritus, significant other systemic diseases with itch) within 12 months prior to Visit 1;
5. Does not meet all study restrictions, including previous/concomitant medication restriction criteria, as described in Section 3.5.5.1;
6. Leucocyte count of $<3.0 \times 10^9/L$ ($<3000/\text{mm}^3$), absolute neutrophil count of $<1.5 \times 10^9/L$ ($<1500/\text{mm}^3$) or absolute lymphocyte count $<0.8 \times 10^9/L$ ($<800/\text{mm}^3$) at Visit 1;
7. Hemoglobin $<11 \text{ g/dL}$ or platelet count $<100,000/\text{mm}^3$ at Visit 1;
8. ALT $>2.0 \times$ the upper limit of normal (ULN) or AST $>2.0 \times$ the ULN at Visit 1;
9. Serum creatinine $>1.5 \times$ the ULN at Visit 1;

10. Hemoglobin A1c (HbA1c) >8.5% at Visit 1;

11. Positive viral serology at Visit 1 for:

- HIV: positive HIV antibodies (Ab),
- HBV: positive hepatitis B surface antigen (HBsAg),
- HCV: positive HCV Ab;

Note: Subjects who test negative for HBsAg and test positive for hepatic B core (HBc) Ab will not be excluded from the study.

12. Positive drug of abuse test results at Visit 1, unless results are due to a medically relevant reason;

Note: Subjects who test positive for only cannabinoids or opiates, and have had no evidence of substance dependence or substance abuse problem that could interfere with study evaluations may participate in the study according to the Investigator's judgment, if all other study restrictions required by the protocol are met.

13. History or presence of substance abuse, drug addiction or alcoholism within 1 year prior to Visit 1;

Note: Alcoholism is defined as the consumption of more than 28 units of alcohol a week (an alcohol unit is defined as 300 mL of beer, 100 mL of wine, or 25 mL of hard liquor).

14. Positive QuantiFERON®-TB Gold Plus test, positive chest radiographic findings for tubercle bacillus (TB) or any other evidence of active or untreated latent TB;

- The QuantiFERON®-TB Gold Plus test should not be performed within 4 weeks from the date of a live vaccination;
- If QuantiFERON®-TB Gold Plus test is indeterminate, a retest is allowed if results can be obtained within the timeframe allowed between Visit 1 and Visit 2. If the retest is also indeterminate, the subject will be excluded from the study;
- Subjects with positive QuantiFERON®-TB Gold Plus test and a history of treated latent TB who have documented evidence of completed adequate treatment at least 12 months prior to Visit 2 may participate in the study, if all other study restrictions required by the protocol are met;
- Subjects who have had household contact with a person with active TB are excluded, unless appropriate and documented prophylactic treatment for TB, as recommended by local guidelines, was completed at least 30 days prior to Visit 2.

15. History of live vaccination within 4 weeks prior to Visit 2 or have a live vaccination planned during the study or within 6 weeks after the last dose of study drug;

16. Have donated or received blood or blood products within 4 weeks prior to Visit 1;

17. History of a clinically-significant infection (e.g., infection that required oral antimicrobial or antiviral therapy) within 4 weeks prior to Visit 2;

Note: Subjects with treated upper respiratory tract infection or urinary tract infection will be permitted if the infection resolved prior to Visit 2.

18. History of opportunistic infections or infection requiring hospitalization or parenteral antibiotic, antiviral, antifungal or antiparasitic therapy within 3 months prior to Visit 2 or history of recurrent infections or conditions predisposing subject to chronic infections (e.g., bronchiectasis, chronic osteomyelitis);

-
19. History or presence of any lymphoproliferative disorder (e.g., Epstein Barr Virus-related lymphoproliferative disorder, lymphoma, leukemia, multiple myeloma) or signs and symptoms suggestive of current lymphatic disease, such as Hodgkin's or Non-Hodgkin's lymphoma;
 20. History or presence of malignancies with the exception of adequately treated or excised non-metastatic basal cell or squamous cell carcinoma of the skin or cervical carcinoma in situ more than 6 months prior to Visit 1;
 21. History of organ transplantation;
 22. History of decompensated heart failure, fluid overload, myocardial infarction, uncontrolled arterial hypertension or evidence of ischemic heart disease or other serious cardiac disease within 12 months prior to Visit 1;
 23. Pregnant or nursing at Visit 1 or Visit 2 or plan to become pregnant or initiate breastfeeding during the study or within 30 days after the last dose of study drug;
 24. History of clinically-significant hypersensitivities (e.g., multiple drug allergies or severe allergic reactions, including angioedema);
 25. History or presence of significant uncontrolled depressive disorder (e.g., manic-depressive disorders, treatment-resistant major depression), history of suicidal ideation or behavior or presence of risk for suicide by Investigator's judgment;
 26. History or presence of any other clinically relevant medical condition or disease or laboratory abnormality including hepatic, renal, gastroenterologic, respiratory, cardiovascular, endocrinologic, neurologic (e.g., epilepsy), psychiatric (e.g., schizophrenia), immunologic (e.g., immunocompromised subjects or subjects with autoimmune conditions other than psoriasis, such as rheumatoid arthritis, systemic lupus erythematosus, type I diabetes), metabolic bone (e.g., osteoporosis) or hematologic (e.g., sickle cell) disease that, in the opinion of the Investigator, may place the subject at unacceptable risk for study participation and may prevent the subject from completing the study (e.g., low life expectancy, high risk of non-compliance) or would interfere with the study conduct or data interpretation, according to the Investigator's judgment;
 27. Cannot communicate reliably with the Investigator (including inability to complete the self-assessment questionnaire) or are unlikely to cooperate with the requirements of the study.

3.4 Removal of Subjects from the Study

A subject will not participate further in the study under the following conditions:

1. Death
2. Adverse Event: a clinical or biological adverse event or intercurrent condition(s), requiring study drug discontinuation, whether or not related to the study drug.

If grade 3 findings (defined as severe or medically significant but not immediately life-threatening; hospitalization or prolongation of hospitalization indicated; disabling; limiting self-care activities of daily living such as bathing, dressing, undressing, feeding self, using the toilet, taking medication, but not bedridden), according to the common terminology criteria for adverse events (CTCAE)¹⁴, are noted in a subject, he/she must be promptly evaluated by the Investigator (e.g., repeat tests, evaluation of the baseline parameters, concomitant medications) for potential withdrawal from the study. Every effort should be made to discuss this with the Medical Monitor prior to final decision, unless not feasible, based on safety considerations.

3. Withdrawal by Subject: subjects have the right to withdraw from the study at any time. However, if a subject withdraws consent because of experiencing an adverse event, the reason for subject termination should be documented as an adverse event.
4. Non-compliance with Study Drug (i.e., <80% or >120% compliance at two consecutive study visits; exceptions on a case-by-case basis may be permitted if approved by Sponsor or designee).

Note: Compliance will be evaluated at every study visit during the Treatment Period. If compliance of <80% or >120% is identified at a study visit, the Investigator or designee should counsel the subject and ensure steps are taken to improve compliance.

5. Inclusion/Exclusion Criteria Not Met: If a subject who did not meet one or more of the study inclusion or exclusion criteria is identified after randomization, the Investigator, Medical Monitor and Sponsor will review that subject profile, including the medical history, prior and concomitant medications, physical examination, vital signs, 12-lead ECGs and clinical laboratory test results. An exception may be permitted on a case-by-case basis if the subject was randomized into the study due to a minor error determined to be of no clinical and/or safety risk to the subject.
6. Protocol Violation: the subject is non-compliant with regard to this protocol (other than the withdrawal criteria 4 and 5 listed above), as determined by Sponsor, Medical Monitor or the Investigator on a case-by-case basis.
7. Lost to Follow-up: the subject does not come for a scheduled visit and site staff makes at least 3 attempts, including a formal letter, to contact the subject over 4 weeks from a scheduled visit with no success.
8. Study Terminated by Sponsor: the Sponsor may suspend or terminate the study or part of the study at any time for any reason.
9. Pregnancy
10. Investigator Decision: the Investigator decides a subject should be discontinued for any reasons other than listed above (actual reason must be documented by site).
11. Other: actual reason must be documented by site.

Subjects who are removed from the study or withdraw consent to participate in the study after receiving at least one dose of study drug will be requested to complete an Early Termination Visit at which time the subject will undergo all the procedures described for Visit 7. Every effort should be made to perform the Visit 7 procedures as soon as possible after the last dose of study drug and the decision of discontinuation is made and prior to any changes made in the subject's anti-psoriasis therapy. Additionally, at approximately 4 weeks after study drug discontinuation, subject should return for a Follow-up Visit, where all procedures described for Visit 8 should be performed.

3.5 Study Procedures

[figure not shown]

Figure 1. Study Schema

Table 1. Schedule of Study Procedures

	Screening Period	Treatment Period							Follow-up Period
Duration/ Study Week (Day) ^a	Up to 4 weeks	Week 0 (Day 1)	Week 2 (Day 14±2)	Week 4 (Day 28±2)	Week 8 (Day 56±4)	Week 12 (Day 84±4)	Week 16 (Day 112±4)	Week 20 (Day 140±4)	
Visit	1	2	3	4	5	6	7	8	
Informed Consent ^b	X								
Inclusion/ Exclusion Criteria	X	X							
Medical History	X	X							
Demographic Information	X								
Review Prior/ Concomitant Medications	X	X	X	X	X	X	X	X	
Physical Exam	X	X	X	X	X	X	X	X	
Vital Signs including Weight	X	X	X	X	X	X	X	X	
Height and Calculate BMI	X								
12-Lead ECG	X	X		X				X	
Chest Radiography ^c	X								
Quantiferon-TB Gold Plus Test	X								
Drugs of Abuse Screen	X								
Viral Serology	X								
FSH ^d	X								
Pregnancy Test ^d	X	X	X	X	X	X	X	X	
HbA1c	X								
Serum Biochemistry	X	X	X	X	X	X	X	X	
Hematology	X	X	X	X	X	X	X	X	
Urinalysis	X	X	X	X	X	X	X	X	
Coagulation	X	X	X	X	X	X	X	X	
Psoriasis Body Surface Area	X	X	X	X	X	X	X	X	
PASI	X	X	X	X	X	X	X	X	
sPGA	X	X	X	X	X	X	X	X	
Skindex 16	X	X	X	X	X	X	X	X	
Itch NRS ^e									
Digital Photography ^f		X					X		
Randomization using IWRS		X							
Access IWRS and Dispense Study Drug ^g		X	X	X	X	X			
Collect Study Drug and Check Compliance ^j			X	X	X	X	X		
Study Drug Administration ^k		X	X	X	X	X			
JTE-451 PK Blood Samples ^l		X		X	X	X	X		
Document Adverse Events ^m	X	X	X	X	X	X	X	X	

Note: All study procedures should be performed at each study visit prior to study drug administration; except for appropriate PK sample collection procedures as discussed below (see [Figure 2](#)). When scheduled at the same time points, ECG and vital sign parameters collection activities should be performed prior to (or at least 15 minutes after) procedures involving venipuncture [REDACTED]

- a. The target day for each visit after randomization will be calculated relative to the date of Visit 2. Every attempt should be made to have the subject attend each visit within the windows specified in the table. The study site is encouraged to make a reminder phone call to the subject before the scheduled visit. However, if a subject is unable to attend a visit within the specified windows, the visit should be scheduled as closely as possible to these windows. A subject should not skip a protocol-specified visit due to scheduling difficulties.
- b. Written informed consent must be obtained prior to performing any study-related procedures including washout of previous medications prior to or at the Screening Visit to participate in the study.
- c. Chest radiography may not be performed if it has been performed within 12 weeks of the Screening Visit and documentation is available for review by the Investigator and inclusion in the subject's file.
- d. At Visit 1, serum pregnancy test will be performed for all female subjects. At Visits 2 through 8 (or Follow-up Visit), urine pregnancy tests will be performed only for female subjects of childbearing potential. At Visit 1, female subjects with a documented history of lack of menses for ≥ 12 consecutive months with no other reversible medical etiology will be considered post-menopausal. Only for the female with a history of lack of menses but onset has been within 12 months prior to Visit 1, an FSH testing is required at Visit 1, then an FSH >40 mIU/mL will be considered post-menopausal, otherwise subject is considered of childbearing potential.
- e. The Itch NRS during a 24-hour recall period will be recorded in the e-diary by the subject once daily from the day of screening through the last visit. Site will dispense the e-diary device at Screening Visit and train the subject on how to use the device.
- f. If collecting photographs is raised as the reason for not participating in the study, the subject still can be part of the study without collecting photographs. Subjects who do not raise this objection will be required to take photographs of four half-body views (i.e., upper anterior, lower anterior, upper posterior and lower posterior).

- [REDACTED]
- [REDACTED]
- i. At Visit 2 through Visit 6, randomized subjects will receive sufficient study drug blister cards for the period between visits. At Visit 7, study drug will not be dispensed. If a subject discontinues study drug prematurely after receiving at least one dose of study drug, the termination should be recorded as soon as possible after the decision has been made.
- j. Subjects will be instructed to bring all used and unused blister cards to each study visit for accountability purposes. Study drug compliance will be calculated by the site at each visit during the Treatment Period starting at Visit 3, based on the number of tablets dispensed or returned by the subject.
- k. Oral administration for 16 weeks starting on the day of randomization at Visit 2, BID, at approximately 12-hour intervals, regardless of meals. On study visit days, subjects should take their scheduled study treatment from their existing study drug supply (if available) at the site, under the supervision of the investigator or designee after all required procedures prior to administration have been performed (except for Visit 7, when no study drug will be administered, as the last dose will be taken the day prior to the visit).
- l. See [Figure 2](#) for a detailed description of PK sampling time points.
- m. Adverse event information will be collected at the specified time points as well as at any time when a site staff member becomes aware of an AE after the subject signs the informed consent for the study. However, stable or improving pre-existing conditions detected through the screening procedures at Visit 1 (e.g., abnormalities in ECG, physical examination, vital signs and laboratory tests) are considered medical history and should be documented accordingly.

[figure not shown]

Figure 2. Dosing and Pharmacokinetic Sample Collection Time

- a. Exact date and time of dose at each visit at the site will be collected.
- b. Exact date and time of the last two doses prior to the pre-dose/trough PK sample collection will be collected.
- c. The pre-dose PK sample collections (i.e., samples obtained prior to the dosing of the study drug at the site) are mandatory in all subjects at all sites. The sample collection date and time will be recorded.
- d. The trough PK sample collections (relative to dosing of the study drug on the day prior to the visit) are mandatory in all subjects at all sites. The sample collection date and time will be recorded.
- e. Three post-dose PK samples per subject (relative to the dosing of the study drug at the site) should be collected from at least 34 randomized subjects. The samples will consist of one sample from 1 to 2 hours window at Week 0 (Visit 2), one sample from 3 to 6 hours window at Week 0 (Visit 2), and one sample from 3 to 6 hours window at Week 4 (Visit 4). The relative sampling time of the two samples of 3 to 6 hours window at Visit 2 and Visit 4 should be separated by at least 1 hour. The sample collection date and time will be recorded.

3.5.1 Informed Consent

Written informed consent must be obtained prior to performing any study-related procedures including washout of previous medications to participate in the study. A copy of the informed consent will be provided to the subject. Washout of previous medications to participate in the study will be started once the subject signs the informed consent regardless of the 28-day window of the Screening Period.

3.5.2 Screening Period

Day -28 (Visit 1) to Day 1 (Visit 2)

Following signing of the informed consent for the study, screening procedures to confirm eligibility may be performed across multiple days, as needed, during the Screening Period. If a subject arrives for a visit not having fasted (fasted at least 10 hours prior to blood and urine sample collection), all study procedures except the blood/urine collection activities may be performed; the blood/urine collection will be rescheduled on a subsequent day within the visit window and the subject will be reminded to fast at least 10 hours.

Please refer to [Table 1](#) for the list of screening procedures to be performed in the study. A one-time repeat of the screening laboratory (except for drugs of abuse and alcohol, and viral serology), vital sign and ECG assessments is permitted, if considered appropriate by the Investigator, except stated otherwise (e.g., up to three-time repeat of blood pressure measurements at the Screening Visit is permitted). The repeat test result(s) will be utilized for subject qualification purposes. If the repeat test results are outside the protocol-required range, the subject should be excluded from the study.

Re-screening of subjects may be permitted on a case-by-case basis, pending discussion and approval by the Medical Monitor.

3.5.3 Double-blind Treatment Period

Day 1 (Visit 2) to Day 112±4 (Visit 7/Week 16)

Please refer to [Table 1](#) for the by-visit list of procedures to be performed in the study during this period.

All visits during the Double-blind Treatment Period, including Visit 2 (Randomization Visit), should be performed under fasted conditions (fasted at least 10 hours prior to blood and urine sample collection). If a subject arrives for a visit not fasted, then all study procedures except the blood/urine collection activities may be performed; the blood/urine collection will be rescheduled on a subsequent day within the visit window and the subject will be reminded to fast at least 10 hours. Exception to this would be Visit 2, at which all study procedures should be completed within the same session, therefore, if the subject is not fasted at Visit 2, the full visit should be rescheduled. Every effort should be made to collect blood/urine samples at similar times throughout the study.

All visits should be performed within the windows specified in [Table 1](#). Every attempt should be made to have the subject attend each visit as scheduled. The site is encouraged to make a reminder phone call to the subject approximately a day or two before the scheduled visit. However, if a subject is unable to attend a visit within the specified windows, the visit should be scheduled as

closely as possible to these windows. A subject should not skip a protocol-specified visit due to scheduling difficulties.

Subjects will be administered the first dose of study drug at the site, upon completion of all pre-dosing procedures and randomization at Visit 2; subsequently, they will be instructed to self-administer study drug BID, at approximately 12-hour intervals, regardless of meals. However, subjects should not take study drug on the day of a study visit until after all study procedures have been completed (except for post-dose PK samples collection as shown in [Figure 2](#)). On study visit days, subjects should take their scheduled study treatment at the site, under the supervision of the investigator or designee after all required procedures prior to administration have been performed (except for Visit 7, when no study drug will be administered, as the last dose will be taken the day prior to the visit). If the subject inadvertently took study drug on the day of the study visit, prior to all required procedures, he/she may complete the visit and the actual date and time of the last dose prior to the PK blood samples collection will be accurately recorded.

Exact date and time of the last two doses prior to the pre-dose/trough PK sample collection at Visits 4 through 7 and the dosing time at the site should be documented at each visit during the Treatment Period (i.e., Visits 2 through 6).

Study drug will not be administered and all remaining study drug will be collected from the subjects at Visit 7.

If a subject discontinues the study prematurely after receiving at least one dose of study drug, an Early Termination Visit should be completed at which all procedures listed for the Visit 7 should be performed, if possible, prior to any changes made in the subject's anti-psoriasis therapy.

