1.3.2 Justification for Study Design

A parallel group, placebo-controlled design will be employed in this study to evaluate the effect of JTE-451 on the efficacy and safety of JTE-451 compared to placebo in subjects with plaque psoriasis. Briefly, upon completion of all protocol-mandated screening procedures, qualified subjects will be randomized at Visit 2 in a 1:1:1 ratio to one of the following three parallel dose groups: JTE-451 200 mg BID (400 mg/day), JTE-451 400 mg BID (800 mg/day) or placebo BID (approximately 50 subjects to be randomized per group) and will receive the double-blind treatment for 16 weeks followed by a 4-week Follow-up Period. To minimize potential confounders in efficacy responses, randomization will be stratified based on prior exposure to biologic therapy (i.e., biologic-naïve vs. biologic-experienced subjects) and body weight (i.e., <90 kg vs. ≥90 kg at Visit 2). No clinically meaningful food effect on the PK of JTE-451 was shown in the single ascending dose study [REDACTED] thus, study drug will be administered regardless of meals. Based on the PK characteristics of the compound, the protocol requires the study drug administration twice a day, at approximately 12-hour intervals. The duration of the double-blind treatment period is sufficient to obtain the proof-of-efficacy for JTE-451 in subjects with plaque psoriasis. The duration of the Follow-up Period is set to approximately 4 weeks; standard duration for similar outpatient studies administered an

investigational product. Based on the PK characteristics of JTE-451, this period is considered conservative, as JTE-451 clears the human body within approximately one day after the last dose.

[figure not shown]
The efficacy parameters assessed in this study are consistent with the standards in the industry in similar psoriasis trials (e.g., PASI, sPGA, BSA).

[REDACTED] To minimize the chances of errors, all calculations of derived parameters will be done by the Sponsor based on the appropriate core data points collected and documented by the Investigators.

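### The Protocol 3.5.3 fasting rule does not exempt PK blood, so an unfasted Visit 7 subject's Week 16 trough can become an off-drug sample, and SAP 6.6.2 has no rule for it

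*Protocol*

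**What the plan says.** **Fasting rule.** Protocol 3.5.3 requires a fast of at least 10 hours at every treatment-period visit. "If a subject arrives for a visit not fasted, then all study procedures except the blood/urine collection activities may be performed". The samples themselves are moved: "the blood/urine collection will be rescheduled on a subsequent day within the visit window and the subject will be reminded to fast at least 10" (the figure is in hours). One visit is treated differently: "Exception to this would be Visit 2, at which all study procedures should be completed within the same session". PK samples are neither named nor exempted.

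**Visit 7 dosing.** The same section places the last dose on the day before Visit 7 and adds: "Study drug will not be administered and all remaining study drug will be collected from the subjects at Visit 7".

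**The trough.** Table 1 and Section 3.5.6.26 schedule PK blood at Visit 7. Figure 2 footnote d (Section 3.5): "The trough PK sample collections (relative to dosing of the study drug on the day prior to the visit) are mandatory in all subjects at" every site.

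**Drug properties.** Section 1.3.2 says that JTE-451 leaves the body within about one day of the last dose. On meals it says: "No clinically meaningful food effect on the PK of JTE-451 was shown".

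**Analysis.** SAP 6.6.2 summarises plasma concentrations by treatment and nominal visit and counts BLQ values as zero. Protocol 3.8.6.1 lists Weeks 2, 4, 8 and 12 for its trough summary and does not list Week 16.

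**The concern.** A site that follows 3.5.3 as written would send an unfasted Visit 7 subject home and draw all blood, PK included, on a later day. By then the subject has had no dose for more than a day and has no tablets left. The sample still carries the Week 16 label, but it measures washout and not the trough of twice-daily dosing. Nothing visible in the SAP would separate it from a true trough. The Week 16 concentration summary would then be pulled down for a reason that has nothing to do with exposure on treatment.

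The documents also give PK no reason to wait for a fast. Dosing is regardless of meals. The procedure sections ask for fasted samples for hematology (3.5.6.13), biochemistry (3.5.6.14) and urinalysis (3.5.6.18), but the PK section (3.5.6.26) does not.

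**Working it through.** **1. Timing.** Inputs from the protocol: dosing about every 12 h, last dose on the day before Visit 7, redraw on a later calendar day. Illustrative clock times (assumed): last dose 20:00, visit 08:00, redraw 08:00 the next day.
- Planned trough: 20:00 to 08:00 = 12 h after the last dose.
- Redraw: 12 + 24 = 36 h after the last dose.
- Lower limit: the whole visit day lies between the last dose and the redraw, so the redraw is more than 24 h after the last dose at any clock times.
- The delay from the scheduled draw can be shorter than 24 h. A 16:00 visit with an 08:00 redraw gives 16 h. Section 3.5.3 asks for samples at similar times of day, which favours about 24 h.
- The window is Day 112±4, that is Days 108 to 116. A visit on Day 108 allows a delay of up to 116 - 108 = 8 days. A visit on Day 116 leaves no later day inside the window.

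**2. Half-life (assumed).** The visible text gives no half-life, so the one-day clearance statement cannot be reproduced. I take clearance in about 24 h to mean roughly 3.4 to 7 half-lives:
- 24 / 3.4 half-lives ≈ 7 h
- 24 / 7 half-lives ≈ 3.4 h

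**3. What remains in the late sample.** With first-order decay, the ratio to the scheduled sample is r = 2^(-delay / half-life).

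| Half-life | Delay 24 h | Delay 16 h |
|---|---|---|
| 3.4 h | 2^(-7.06) = 0.8% | 2^(-4.71) = 4% |
| 4.8 h | 2^(-5) = 3% | 2^(-3.33) = 10% |
| 7 h | 2^(-3.43) = 9% | 2^(-2.29) = 20% |

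**4. Effect on the Week 16 arithmetic mean.** If a fraction f of subjects is affected and they otherwise resemble the rest, the mean falls by f × (1 - r). For a 24 h delay:
- f = 10%: 0.10 × (1 - 0.09) = 9.1% to 0.10 × (1 - 0.008) = 9.9%
- f = 2%: 0.02 × (1 - 0.09) = 1.8% to 0.02 × (1 - 0.008) = 2.0%

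SAP 6.6.2 also reports the median, which a few low values hardly move.

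**5. The passages side by side.** For an unfasted Visit 7 subject, three instructions cannot all be met: postpone blood collection (3.5.3), give no further dose and take the drug back (3.5.3), and draw a trough tied to the previous day's dose (Figure 2 footnote d).

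**The case against.** The strongest reply is that the fasting rule was never meant for PK. It speaks of blood and urine collection in general, the fasting requirement is attached test by test elsewhere, and PK timing is sent to Figure 2 and the laboratory manual. A site could treat the specific PK rule as overriding the general one. Figure 2 is not shown and the manual is not available, so either may settle the matter. This stands as a limit on certainty: PK is caught by general wording, not by name. It does not remove the gap, because 3.5.3 makes an exception for Visit 2 and none for PK.

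Other points that stand:
- 3.5.3 permits, but does not require, the other procedures to go ahead. A site could move the whole visit and keep the subject on drug. Nothing tells it to.
- The non-fasting rate is unknown. Subjects are told to fast and sites are encouraged to make reminder calls, so it may be small.
- Protocol 3.8.6.1 omits Week 16 from its trough summary. That list does not match the schedule, however: it includes Week 2, when no PK sample is taken, and SAP 6.6.2 excludes no visit.
- Exact dose and sample times are recorded, so late samples can be identified and population PK can use them. Weeks 4, 8 and 12 supply other pre-dose samples.
- The PK population requires a usable concentration but does not define the term. It applies to the subject, not to each sample.

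A reader might infer two stronger claims. The first is that the link between Week 16 exposure and response is broken. The exposure-response text is not visible (Protocol 3.8.6.2 is an empty heading), so this cannot be said. The second is that troughs at Visits 4 to 6 are lost in the same way, or that a dose is held across days. Dosing continues at those visits, so a valid trough can still be drawn later. The sentence "subjects should not take study drug on the day of a study visit until after all study procedures have been completed" concerns the visit day only, and the next sentence refers to procedures required before administration. What remains there is a minor wording conflict.

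**Conclusion.** The point holds for Visit 7, as a gap in wording with a limited effect on the PK summary. Read as written, 3.5.3 moves an unfasted subject's Week 16 PK sample to a time when, by the protocol's own statement, the drug has largely cleared, and the SAP does not say what to do with it. The downward bias in the nominal Week 16 mean is close to proportional to the share of subjects affected. It rests on three assumptions: a half-life of 3.4 to 7 h, a delay of about 24 h, and affected subjects who resemble the rest. With a 16 h delay it is somewhat smaller. The non-fasting rate sets the actual size and is not given. Primary and secondary efficacy, safety results and error rates do not depend on it. It is worth correcting because the remedy is short and PK loses nothing by it.

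**What to change.** **Protocol 3.5.3 and Table 1 (PK footnote).** State that PK samples are drawn at the scheduled visit whether or not the subject is fasted, and that only the fasting laboratory and urine samples are rescheduled. Carry the same wording into the laboratory manual.

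**SAP 6.6.2.** Flag, or exclude from the nominal-visit summary, Week 16 samples not drawn on the day after the last dose, using the recorded dose and sample times.

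**Visits 4 to 6.** Reconcile the sentence on taking study drug after all procedures with the rescheduling sentence, so that sites know how the two work together. This is a minor wording point, and the choice belongs to the sponsor.

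**Cost.** One protocol sentence, one SAP sentence, and a second needle stick in the few subjects who arrive unfasted.
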